Hypertension: Hypertension (HTN) should be managed per institutional standards and appropriate medical guidelines. trebananib should be held for systolic BP > 200 mmHg or diastolic BP > 110 mmHg, or symptomatic hypertension. trebananib may be resumed at the pre-hold dose upon resolution of symptomatic HTN, systolic BP ≤ 140 mmHg and diastolic BP ≤ 90 mmHg, or returned to participant's baseline blood pressure. If the participant's BP is elevated upon first reading, measurements should be confirmed with a repeat measurement.

For any grade of hypertensive crisis or hypertensive encephalopathy, permanently discontinue trebananib.

Hypokalemia: Participants should have their serum potassium checked as outlined in the Section 9 and managed per institutional guidelines. If hypokalemia is present, replacement should be managed with either oral and/or parenteral replacement, according to institutional practice and to the degree of hypokalemia present. It is recommended that the participant's serum potassium level should be maintained within the normal range, as much as possible, during study treatment. Isolated hypokalemia without clinical sequelae should not be reported as an adverse event.

Pleural Effusion and Ascites: Pleural effusion and ascites should be graded according to CTCAE v4.0. However, since trebananib is known to cause or worsen pre-existing pleural effusions and ascites, these adverse events should be managed as noted below:

Life-threatening pleural effusions or ascites:

- Institute emergency measures per institutional guidelines
- Permanently discontinue trebananib

For all non-life-threatening pleural effusion or ascites:

- Treat per institutional guidelines which may include,

- o non-investigational diuretics,
- o thoracentesis, chest tube drainage or paracentesis
- o pleurodesis
- Investigators should document each paracentesis and /or thoracentesis that occurs while a participant is on study.

Additional toxicities to permanently discontinue trebananib for:

- Gastrointestinal perforation
- Compromised wound healing
- Fistula formation
- Nephrotic syndrome or thrombotic microangiopathy (TMA)
- Reversible posterior leukoencephalopathy syndrome (RPLS)
- Ascites or pleural effusion requiring therapeutic intervention

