5.5 Definition of Dose-Limiting Toxicity (DLT)

Dose-limiting toxicities (DLTs) will be assessed during the first 3 weeks of treatment so that labs and other evaluations taken at the end of the first cycle (start of the second cycle) are included in the assessment period. A DLT is defined as an adverse event that is (a) related to pembrolizumab and/or trebananib with an attribution of possible, probable, or definite, and (b) occurs during and/or begins during the first 3 weeks of the study treatment and (c) meets any of the following criteria:

Hematological toxicities

- A Grade 4 hematological toxicity unrelated to an underlying medical condition
- Arterial thromboembolic event

Non-hematological toxicities:

- A non-hematological toxicity of grade 3 unrelated to an underlying medical condition
- Eye pain of grade 2 or higher.
- Urine protein: creatinine > 3.5 or >2g protein on 24hour urine collection
- Two delays of treatment (not due to scheduling non-compliance) each lasting more than 10 days within 4 cycles of drug.

Exclusions to Dose limiting toxicities:

- Grade 3 electrolyte toxicities that can be corrected to Grade 1 or less within 24 hours will not be considered dose limiting.
- Grade 3 hypertension that can be controlled with oral medications and does not require treatment delay for > 7 days will not be considered a DLT.
- Grade 3 diarrhea that can be corrected to Grade 1 or less within 48 hours after anti-diarrhea medication will not be considered dose limiting.
- Grade 3 nausea and vomiting that can be corrected to Grade 1 or less within 48 hours after anti-emetic therapy will not be considered a DLT.

- Grade 3 rise in creatinine that can be corrected to Grade 2 or less after 2 liters of intravenous fluids within 24 hours will not be considered dose limiting.
- Grade 3 elevation in AST/ALT if AST/ALT levels were <1.5 times the baseline level will not be considered a DLT.
- Grade 3 elevation on ALP (Alkaline phosphatase) will not be considered a DLT.
- Grade 3 lymphopenia will not be considered a DLT.
- Grade 3 rash that returns to \leq grade 2 after 1 week of symptomatic treatment will not be considered a dose limiting toxicity.

Management and dose modifications associated with the above adverse events are outlined in Section 5.3.3.

Dose escalation will proceed within each cohort according to the following schema. Dose-limiting toxicity (DLT) is defined above.

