6. ADVERSE EVENTS: LIST AND REPORTING REQUIREMENTS

An adverse event is defined as any untoward medical occurrence in a patient or clinical investigation participant administered a pharmaceutical product and which does not necessarily have to have a causal relationship with this treatment. An adverse event can therefore be any unfavorable and unintended sign (including an abnormal laboratory finding, for example), symptom, or disease temporally associated with the use of a medicinal product or protocol-specified procedure, whether or not considered related to the medicinal product or protocol-specified procedure. Any worsening (i.e., any clinically significant adverse change in frequency and/or intensity) of a preexisting condition that is temporally associated with the use of the Merck's product, is also an adverse event.

Changes resulting from normal growth and development that do not vary significantly in frequency or severity from expected levels are not to be considered adverse events. Examples of this may include, but are not limited to, teething, typical crying in infants and children and onset of menses or menopause occurring at a physiologically appropriate time.

Merck and Amgen products includes any pharmaceutical product, biological product, device, diagnostic agent or protocol-specified procedure, whether investigational (including placebo or active comparator medication) or marketed, manufactured by, licensed by, provided by or distributed by Merck and Amgen for human use.

Adverse events may occur during the course of the use of Merck or Amgen product in clinical trials, or as prescribed in clinical practice, from overdose (whether accidental or intentional), from abuse and from withdrawal.

Progression of the cancer under study is not considered an adverse event.

All adverse events that occur after the consent form is signed but before presenting for cycle 1 day 1 must be reported by the investigator ONLY if they cause the participant to be excluded from the trial, or are the result of a protocol-specified intervention, including but not limited to washout or discontinuation of usual therapy, diet, placebo treatment or a procedure.

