From the time of cycle 1 day 1 through 30 days following cessation of treatment, all adverse events must be reported by the investigator. Such events will be recorded at each examination on the Adverse Event case report forms/worksheets. The reporting timeframe for adverse events meeting any serious criteria is described in section 6.3 The investigator will make every attempt to follow all participants with non-serious adverse events for outcome.

Adverse events will not be collected for participants during the pre-screening period (for determination of archival tissue status) as long as that participant has not undergone any protocol-specified procedure or intervention.

6.1 Definition of an Overdose for Pembrolizumab and Reporting of Overdose to the Sponsor and to Merck

For purposes of this trial, an overdose of pembrolizumab will be defined as any dose of 1,000 mg or greater (≥ 5 times the indicated dose). No specific information is available on the treatment of overdose of pembrolizumab. Appropriate supportive treatment should be provided if clinically indicated. In the event of overdose, the participant should be observed closely for signs of toxicity. Appropriate supportive treatment should be provided if clinically indicated.

If an adverse event(s) is associated with (“results from”) the overdose of a Merck product, the adverse event(s) is reported as a serious adverse event, even if no other seriousness criteria are met.

If a dose of Merck’s product meeting the protocol definition of overdose is taken without any associated clinical symptoms or abnormal laboratory results, the overdose is reported as a non-serious Event of Clinical Interest (ECI), using the terminology “accidental or intentional overdose without adverse effect.”

All reports of overdose with and without an adverse event must be reported within 24 hours to the IND holder and within 2 working days to Merck Global Safety. (Attn: Worldwide Product Safety; [contact])

6.2 Reporting of Pregnancy and Lactation to the Sponsor and to Merck and Amgen

Although pregnancy and lactation are not considered adverse events, it is the responsibility of investigators or their designees to report any pregnancy or lactation in a participant (spontaneously reported to them) that occurs during the trial.

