14.7 Safety Analysis

Safety data will be presented for all patients who receive at least one dose of either of the study drugs. All adverse events recorded during the trial will be summarized and presented by disease cohort or dose level. The incidence of events that are new or worsening from the time of first dose of treatment will be summarized by dose level or disease cohort, system organ class and/or preferred term, severity (based on CTCAE V4 grade), type of adverse event, and relation to study treatment. Deaths reportable as SAEs and non-fatal serious adverse events will be listed by patient and tabulated by primary system organ class, and type of adverse event.

Safety data from the expansion cohorts will be used to further characterize the safety profile of the drug combination and evaluate the toxicity of the MTD from the dose escalation. We assume that toxicities will be similar for each of the expansion cohorts; however, we will summarize safety data in both the aggregate and by cohort to allow for different adverse event types. Late toxicities observed and assessed as treatment related in the expansion cohort will be monitored. If two or more are observed, enrollment in the expansion cohort will be halted for further review and changing the RP2D will be considered. Given that trebananib is limited in use during only the first 12 weeks (4 cycles), we anticipate there is less chance that the combination of trebananib plus pembrolizumab will exhibit late toxicity in comparison to pembrolizumab given alone.

The following table summarizes the probability of observing at least one patient with a treatment-related toxicity for varying true, but unknown, incidence rates. Estimates in the table are based on individual expansion cohorts of size 12, and also for all 48 patients treated at the MTD.

Underlying incidence rate of treatment-related toxicity	Probability of 1 or more of 12 with treatment-related toxicity	Probability of 1 or more of 48 with treatment-related toxicity
0.01	0.11	0.38
0.05	0.46	0.91
0.10	0.72	0.99
0.15	0.86	>0.99
0.20	0.93	>0.99
0.25	0.97	>0.99

For each expansion cohort of size 12, the probability of observing at least one patient with a dose-related toxicity is greater than 0.70 if the incidence rate of that toxicity is 0.10 or higher. For the aggregated safety data, there is greater than 0.90 probability of observing a toxicity if the incidence rate is 0.05 or higher.

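### Section 5.3.3.2 keeps isolated hypokalemia without sequelae out of adverse event reporting at any grade, in conflict with Sections 5.5, 5.12 and 6, so severe laboratory cases can drop out of the safety tables

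*Combined protocol and SAP*

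**What the plan says.** The hypokalemia paragraph of Section 5.3.3.2 has potassium monitored on the study calendar and replaced according to local practice. It ends with a reporting instruction: "Isolated hypokalemia without clinical sequelae should not be reported as an adverse event". The instruction names no grade, and the protocol nowhere defines clinical sequelae.

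Four other places bear on the same event:

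- Section 6 defines an adverse event to include "any unfavorable and unintended sign (including an abnormal laboratory finding, for example), symptom, or disease". From Cycle 1 Day 1 until 30 days after treatment ends, "all adverse events must be reported by the investigator".
- Section 5.5 begins its definition with "A DLT is defined as an adverse event that is (a) related to pembrolizumab and/or trebananib". One criterion is "A non-hematological toxicity of grade 3 unrelated to an underlying medical condition". Among the exclusions is "Grade 3 electrolyte toxicities that can be corrected to Grade 1 or less within 24 hours will not be considered dose limiting".
- Section 5.12 places drug-related Grade 3 or 4 electrolyte abnormalities in its list of unacceptable adverse events. It adds that those needing nothing beyond electrolyte replacement do not force treatment to stop.
- Section 14.7 sets the analysis: "All adverse events recorded during the trial will be summarized and presented by disease cohort or dose level".

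**The concern.** Safety and tolerability are the primary objective of both parts (Section 1.2), so the adverse event record is the primary data. A reporting exception without a grade limit lets two investigators handle the same severe laboratory value differently while each follows the protocol. One leaves it off the form under Section 5.3.3.2; the other records it under Section 6.

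Two results depend on that choice. The Section 14.7 tables could show fewer Grade 3 or 4 hypokalemia events than occurred. In Part 1, the DLT rate of Section 14.5 could have been understated, because Section 5.5 makes every DLT an adverse event first. Hypokalemia is one of the toxicities that the trebananib section manages by name, so the question is not remote.

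**Working it through.** The finding comes from the text, so the main check is to follow one hypothetical patient through the sections. Suppose that at Cycle 1 Day 8 the potassium is Grade 3, nothing else is abnormal, there are no symptoms, the investigator judges a drug relation possible, and the value cannot be corrected within a day.

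1. Section 5.3.3.2: not to be reported as an adverse event.
2. Section 6: an abnormal laboratory finding after Cycle 1 Day 1 is an adverse event and must be reported.
3. Section 5.5: the event is related, falls in the first three weeks, meets the Grade 3 non-hematological criterion and fails the electrolyte exclusion. By implication it is a DLT, provided it is treated as an adverse event. The exclusion would have no purpose if electrolyte events could not otherwise be DLTs.
4. Section 5.12: a drug-related abnormality of this grade is discussed as an adverse event.
5. Section 14.7: it is counted only if recorded.

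Steps 1 and 2 cannot both be followed, and step 3 depends on which is. If the same value appears in Cycle 3, no DLT question arises and only step 5 is affected.

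Does another planned output recover the case? Section 6.4 includes laboratory results in the medical review of safety, but what it tabulates is adverse event incidence. Section 14.7 plans no laboratory-grade table. Section 14.4 summarizes dose reductions and delays. However, the general Grade 3 or 4 hold rule in Section 5.3.3.2 covers toxicities not already named there, and hypokalemia is named, so a case need not appear as a delay.

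No size can be computed, because the documents give no hypokalemia rate. The following shows sensitivity only.

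*Detection.* The Section 14.7 table uses 1 − (1 − p)^n and reproduces:

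- p = 0.05: 0.460 for n = 12 and 0.915 for n = 48 (plan: 0.46 and 0.91; the unrounded second value is 0.9147).
- p = 0.10: 0.718 and 0.994 (plan: 0.72 and 0.99).

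If a share h of cases goes unrecorded, p becomes p(1 − h). For a toxicity with assumed true incidence 0.10:

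| h | n = 12 | n = 48 |
|---|---|---|
| 0 | 0.718 | 0.994 |
| 0.5 | 0.460 | 0.915 |
| 0.75 | 0.262 | 0.703 |
| 1 | 0 | 0 |

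*Dose escalation.* Under Table 2 of Section 5.1, a dose level with true DLT probability p passes to the next level with probability (1 − p)^3 + 3p(1 − p)^5. At p = 0.30 this is 0.343 + 0.151 = 0.494. If a share of DLTs were unrecorded hypokalemia, the pass probability would be:

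- 10% hidden (p = 0.27): 0.557
- 25% hidden (p = 0.225): 0.654
- 50% hidden (p = 0.15): 0.814

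In a full cohort of six, one uncounted DLT turns 2 of 6 into 1 of 6, which crosses the line in Table 2. Every value of p and h in these two illustrations is assumed.

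**The case against.** The exception is narrow. It covers only hypokalemia that is both isolated and without sequelae. The general scale in Section 6.4 associates Grade 3 with hospitalization and Grade 4 with life-threatening consequences, so many such cases may have sequelae and stay reportable. An admission would also make the event serious under Section 6.3.1. This stands, and a reader who concluded that severe hypokalemia as a whole vanishes from the record would go too far. It does not empty the affected group: the same scale also allows Grade 3 for a severe or medically significant event, and sequelae is left undefined.

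A reader might also infer that such a case can never be a DLT. The documents do not support that. Section 5.3.3.2 says not to report the event; it does not say the event is not an adverse event. Section 5.5 puts end-of-cycle laboratory values inside the DLT window and has its own electrolyte rule, so an investigator could still have counted it. A DLT further requires at least possible attribution and timing in the first three weeks, and its exclusion turns on whether the value can be corrected, which replacement may often achieve. The conflict is unresolved; it is not settled in favor of non-reporting.

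A reader might also put a number of affected patients on this. Nothing in the documents supports a rate, and hypokalemia is not in the Section 2.3.2.2 list of overlapping toxicities. Nor is there any sign that a hypokalemia DLT was actually missed in Part 1. Both points stand. Neither removes the contradiction, nor does either supply a table that would show whether cases occurred.

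**Conclusion.** The reporting instruction in Section 5.3.3.2 conflicts with Sections 5.5, 5.12 and 6, and the protocol does not say which prevails. Isolated Grade 3 or 4 hypokalemia without sequelae can therefore be absent from the Section 14.7 tables, and in Part 1 could have been absent from the DLT count.

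The size is unknown because no rate is given and the boundary of sequelae is undefined. Dose finding is complete and the recommended dose is set, so the live effect is mainly on the Part 2 safety tables, which are planned for 12 + 37 + 4 = 53 expansion patients. The DLT effect is retrospective and only possible. It rests on reading the electrolyte exclusion together with the Grade 3 criterion to mean that an uncorrectable Grade 3 value counts. The documents give no ground for saying that the recommended dose is wrong. The point merits correction because it touches the primary objective and the data needed to close it are already collected.

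**What to change.** Reconcile Sections 5.3.3.2, 5.5, 5.12 and 6 on reporting, so that the hypokalemia exception does not remove events that the DLT and adverse event sections treat as reportable. State what counts as sequelae. Which DLT rule should prevail is for the sponsor and investigators to settle; this point does not decide it, and potassium replacement and dosing are not affected.

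Add to Section 14.7 a table of worst post-baseline potassium grade by dose level and disease cohort, and state how the grade is derived from the laboratory value. Potassium is part of the chemistry panel (Table 14 in Section 10.3.2.5). The calendar in Section 9 has the panel drawn at every induction treatment visit, on Day 1 of each later cycle, at end of treatment and at safety follow-up. Include patients already treated, and check the table against the recorded Part 1 DLT assessments.

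The cost is a wording change, one extra table, a few added adverse event entries and possibly a slightly higher reported toxicity rate. No new sampling is needed.

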5.4 Criteria to Resume Treatment

For non-autoimmune or inflammatory events, patients may resume treatment with study drug when the drug-related AE(s) resolve to Grade \leq 1 or baseline value, with the following exceptions:

- Patients may resume treatment in the presence of Grade 2 fatigue.
- Patients with baseline Grade 1 AST/ALT or total bilirubin who require dose delays for reasons other than a 2-grade shift in AST/ALT or total bilirubin may resume treatment in

the presence of Grade 2 AST/ALT OR total bilirubin.

- Non-drug-related toxicity including hepatic, pulmonary toxicity, diarrhea, or colitis, must have resolved to baseline before treatment is resumed.
- Drug-related endocrinopathies (not including drug-related adrenal insufficiency or hypophysitis) adequately controlled with only physiologic hormone replacement may resume treatment after replacement correction and clinically stable regimen.

If the criteria to resume treatment are met, the patient should restart treatment no sooner than the next scheduled time point per protocol. However, if the treatment is delayed past the next scheduled time point per protocol, the treatment should resume at the earliest convenient point that is within the 12 week delay period.

If treatment is delayed >12 weeks, the patient must be permanently discontinued from study therapy, except as specified in Section 5.12 (Duration of Therapy).

5.5 Definition of Dose-Limiting Toxicity (DLT)

Dose-limiting toxicities (DLTs) will be assessed during the first 3 weeks of treatment so that labs and other evaluations taken at the end of the first cycle (start of the second cycle) are included in the assessment period. A DLT is defined as an adverse event that is (a) related to pembrolizumab and/or trebananib with an attribution of possible, probable, or definite, and (b) occurs during and/or begins during the first 3 weeks of the study treatment and (c) meets any of the following criteria:

Hematological toxicities

- A Grade 4 hematological toxicity unrelated to an underlying medical condition
- Arterial thromboembolic event

Non-hematological toxicities:

- A non-hematological toxicity of grade 3 unrelated to an underlying medical condition
- Eye pain of grade 2 or higher.
- Urine protein: creatinine > 3.5 or >2g protein on 24hour urine collection
- Two delays of treatment (not due to scheduling non-compliance) each lasting more than 10 days within 4 cycles of drug.

Exclusions to Dose limiting toxicities:

- Grade 3 electrolyte toxicities that can be corrected to Grade 1 or less within 24 hours will not be considered dose limiting.
- Grade 3 hypertension that can be controlled with oral medications and does not require treatment delay for > 7 days will not be considered a DLT.
- Grade 3 diarrhea that can be corrected to Grade 1 or less within 48 hours after anti-diarrhea medication will not be considered dose limiting.
- Grade 3 nausea and vomiting that can be corrected to Grade 1 or less within 48 hours after anti-emetic therapy will not be considered a DLT.

- Grade 3 rise in creatinine that can be corrected to Grade 2 or less after 2 liters of intravenous fluids within 24 hours will not be considered dose limiting.
- Grade 3 elevation in AST/ALT if AST/ALT levels were <1.5 times the baseline level will not be considered a DLT.
- Grade 3 elevation on ALP (Alkaline phosphatase) will not be considered a DLT.
- Grade 3 lymphopenia will not be considered a DLT.
- Grade 3 rash that returns to \leq grade 2 after 1 week of symptomatic treatment will not be considered a dose limiting toxicity.

Management and dose modifications associated with the above adverse events are outlined in Section 5.3.3.

Dose escalation will proceed within each cohort according to the following schema. Dose-limiting toxicity (DLT) is defined above.

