5. TREATMENT PLAN

5.1 Treatment Regimen

This is a prospective trial which will accrue participants with solid tumors to evaluate the safety, clinical, and immunological effect of the combination of pembrolizumab and trebananib. The treatment will include an induction phase of pembrolizumab and trebananib for 4 cycles (12 wks) followed by pembrolizumab alone for up to 2 years. This trial will be conducted in 2 parts:

Part I will use a standard 3+3 dose escalation design in all solid tumors (refer to Table 2. Dose escalation will begin in dose cohort +1 (refer to Table 3). If two or more patients in dose cohort +1 experience a DLT, the next cohort of patients will be enrolled into dose cohort -1. Should dose cohort -1 prove too toxic (i.e. two or more patients experience a DLT), enrollment to the study will stop. If the toxicity profile of dose cohort +1 is acceptable per the escalation decision rules in Table 2, the next cohort will be enrolled into dose cohort +2. Should dose cohort +2 have acceptable toxicity per the escalation decision rules in Table 2, that will be the RP2D; otherwise, dose cohort +1 will be the RP2D.

Table 2. Dose Escalation Schema

Number of Patients with DLT at a Given Dose Level	Escalation Decision Rule
0 out of 3	Enter 3 patients at the next dose level.
≥ 2	Dose escalation will be stopped. This dose level will be declared the maximally administered dose (highest dose administered). Three (3) additional patients will be entered at the next lowest dose level if only 3 patients were treated previously at that dose.
1 out of 3	Enter 3 more patients at this dose level. 
 • If 0 of these 3 patients experience DLT, proceed to the next dose level. • If 1 or more of this group suffer DLT, then dose escalation is stopped, and this dose is declared the maximally administered dose. Three (3) additional patients will be entered at the next lowest dose level if only 3 patients were treated previously at that dose.
≤ 1 out of 6 at highest dose level below the maximally administered dose	This is generally the recommended phase 2 dose. At least 6 patients must be entered at the recommended phase 2 dose.

Table 3. Part I Dose Escalation Schedule

Dose Cohort	Pembrolizumab every 3 weeks IV	Trebananib weekly IV	N
- 1	200mg	3 mg/kg	3+3
+1	200mg	15 mg/kg	3+3
+2	200mg	30 mg/kg	3+3

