5.6 Definition of Maximum Tolerated Dose

The MTD will be based on the assessment of DLTs as defined in section 5.5 and will not exceed the 30mg/kg trebananib weekly dose. The MTD will be defined as the dose at which fewer than one-third of participants experience a DLT to pembrolizumab and trebananib.

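### The general non-hematological DLT criterion names Grade 3 alone, so on a literal reading a related Grade 4 or 5 event never recorded at Grade 3 is not a DLT

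*Combined protocol and SAP*

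**What the plan says.** Section 5.5 sets three conditions for a DLT, all required: (a) at least a possible relation to either drug; (b) timing, namely that the event "occurs during and/or begins during the first 3 weeks of the study treatment"; and (c) at least one criterion from a list.

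- **Hematological list:** Grade 4 toxicity, and any arterial thromboembolic event.
- **Non-hematological list:** the general line "A non-hematological toxicity of grade 3 unrelated to an underlying medical condition", then "Eye pain of grade 2 or higher", a urine protein threshold, and "Two delays of treatment (not due to scheduling non-compliance) each lasting more than 10 days within 4 cycles of drug".

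Nine exclusions follow, all for Grade 3 events; an example is "Grade 3 diarrhea that can be corrected to Grade 1 or less within 48 hours".

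Section 5.6 depends on this definition: "The MTD will be based on the assessment of DLTs as defined in section 5.5", and "The MTD will be defined as the dose at which fewer than one-third of participants experience a DLT". In Section 5.1, Table 2 drives the 3+3 steps by DLT count and adds "At least 6 patients must be entered at the recommended phase 2 dose". Section 14.5 makes the proportion with DLT in each escalation cohort a reported endpoint.

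**The concern.** The general line fixes a single grade where a minimum grade is needed. No other text supplies the higher grades: Table 2 and Sections 5.6, 14.2 and 14.5 all use the term DLT without a grade, and Section 5.6 refers back to 5.5. The most severe outcome, a related death from a non-hematological cause, can therefore fall outside the definition while an uncorrected Grade 3 diarrhea falls inside it.

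Such events are plausible here. Section 2.3.2.2 reports that the one DLT in an earlier weekly trebananib dose-escalation study was a respiratory arrest at 30 mg/kg, the trebananib dose since chosen for Part II. Its grade is not given, but an event of that kind could be first recorded at Grade 4 or 5.

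At stake are the DLT rate to be reported per dose cohort and the stated basis for the MTD and the recommended dose. Any error would make the dose look safer than it was.

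**Working it through.** **1. Which events the literal wording misses.** Section 6.4 requires every change of grade within an episode to be recorded, and condition (b) is met if the event begins in the first 3 weeks. For a related non-hematological event starting in the window:

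| Grade path | Recorded at Grade 3? | Meets the general line? |
|---|---|---|
| 3 only | Yes | Yes, unless excluded |
| 2, 3, 4 | Yes | Yes |
| 4, 3, 2 | Yes | Yes |
| 4, then 2 or below | No | No |
| 4, then 5 | No | No |
| 5 from the start | No | No |

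The gap is the last three rows.

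**2. Whether another line catches them.** An arterial thromboembolic event counts at any grade, and eye pain and heavy proteinuria have their own lines. The delay line helps little: it looks across 4 cycles (12 weeks) while condition (b) allows 3, two delays of more than 10 days exceed 20 of those 21 days, and a patient who has died cannot have treatment delays. Events resting on the general line alone stay uncounted.

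**3. What was meant.** The eye pain line, directly after the general one, states an open upper limit. All nine exclusions relieve Grade 3 events only, which makes sense if Grades 4 and 5 count without exception.

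**4. Size.** The documents give no Part I event counts, so no event rate is assumed. Inputs are the cohort sizes (3, or 6 after expansion; Section 14.2 plans 6 to 12 patients in all) and the Section 5.6 limit of below 1/3.

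Fall in the reported rate per uncounted patient = 1/n:

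- n = 6: 1/6 = 16.7 percentage points
- n = 3: 1/3 = 33.3 percentage points

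| True count | Literal count | True reading | Literal reading |
|---|---|---|---|
| 1/6 = 16.7% | 0/6 = 0% | Meets 5.6 | Meets 5.6 |
| 2/6 = 33.3% | 1/6 = 16.7% | Fails 5.6 (not below 1/3); Table 2 stops | Meets 5.6; Table 2 proceeds |
| 1/3 | 0/3 | Table 2 adds 3 patients | Table 2 escalates |
| 2/3 | 1/3 | Table 2 stops | Table 2 adds 3 patients |

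At cohort +2, the highest planned level, there is no further escalation to stop. A true 2/6 there would mean unacceptable toxicity, and under Section 5.1 the recommended dose would then be that of cohort +1 (15 mg/kg).

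**The case against.** The strongest reply is that nobody would apply the line literally. A rule that counts uncorrected Grade 3 diarrhea but not a drug-related death is absurd, and naming only the lowest grade looks like a drafting habit, since the hematological line says Grade 4 without Grade 5. The recommended dose is set, so new wording cannot alter any escalation step. Nothing shows an event was missed, and the 2/6 case needs one counted DLT, a second patient with an event in the gap, and investigators who read the text literally. Severe events also surface elsewhere: expedited reporting (Section 6.3.1), safety committee review (13.2), and the severity tables and serious event listings of 14.7.

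Most of this stands, and it limits the point to a wording error with a reporting consequence. Two things remain. Evident intent does not document how Part I events were adjudicated. And the other safety reporting reveals a severe event without correcting the DLT count on which Sections 14.5 and 5.6 rely. The parallel gap in the hematological line widens the repair.

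**Conclusion.** The point holds. As written, Section 5.5 leaves out a related non-hematological event never recorded at Grade 3 and not caught by a specific line. Grade 3 or higher was clearly intended.

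No undercount is shown, and the recommended dose is not shown to be wrong. The possible effect is bounded by cohort size: 16.7 points per uncounted patient with six, 33.3 with three. Only a shift such as 2/6 to 1/6 would change whether a six-patient cohort meets Section 5.6. This rests on the text alone, on grade changes being recorded as Section 6.4 requires, and on no assumed event rates. It is a minor correction worth making before the DLT rates are reported.

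**What to change.** 1. In Section 5.5, insert *or higher* after *grade 3* in the general non-hematological line. Make the matching change after *Grade 4* in the hematological line, so that Grade 5 is covered there too.
2. Before reporting the Section 14.5 DLT rate, check all recorded Grade 4 and 5 non-hematological events, and Grade 5 hematological events, in the Part I patients against conditions (a) and (b).
3. If any were left out, re-tabulate the DLT rate for each dose cohort.
4. State the result in the report, including whether the recommended dose level still meets Section 5.6.

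The cost is a few words and one review of data already recorded for a planned 6 to 12 patients. If nothing was missed, one sentence in the report settles it. The only downside is that a reported DLT rate may become less favourable.
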